#### **5.7.4.5 Sustained Pain Freedom from 2 to 24 Hours**

Sustained pain freedom is assessed using the number of mITT subjects that experienced no headache pain (response of 0 on Likert scale) at all time points from 2 through 24 hours post-dose. Subjects with missing pain scores at 1 or fewer time points, given that they have responses of no pain (response of 0 on 4-point Likert scale) at all other time points including the 2 and 24 hour post-dose time points will be considered as successes. Subjects with responses missing at greater than 1 post-dose time point, missing data at the 2 or 24 hour time point, or with any pain score greater than 0 will be considered as failures.

The results to be presented for the analysis include those described in items (a) through (e) for the primary analysis of pain freedom (Section 5.7.3.1). In this case, the “risk” is the probability of sustained pain freedom from 2 to 24 hours.

#### **5.7.4.6 Sustained Pain Freedom from 2 to 48 Hours**

Sustained pain freedom is assessed using the number of mITT subjects that experienced no headache pain (response of 0 on Likert scale) at all time points from 2 through 48 hours post-dose. Subjects with missing pain scores at no more than 1 time point, given that they have responses of no pain (response of 0 on Likert scale) at the 2, 24, and 48 hour time points will be considered as successes. Subjects with responses missing at greater than 1 time point; missing data at the 2, 24, or 48 hour time point; or with any pain score greater than 0 will be considered as failures.

The results to be presented for the analysis include those described in items (a) through (e) for the primary analysis of pain freedom (Section 5.7.3.1). In this case, the “risk” is the probability of sustained pain freedom from 2 to 48 hours.

#### **5.7.4.7 Sustained Pain Relief from 2 to 24 Hours**

Sustained pain relief is assessed using the number of mITT subjects who experience no or mild headache pain (responses of either 0 or 1 on 4-point Likert scale) at all time points from 2 through 24 hours post-dose. Subjects with missing pain scores at no more than 1 time point, given that they have responses of no or mild pain at the 2 and 24 hour time points will be considered as successes. Subjects with responses missing at more than 1 time point, with missing data at the 2 or 24 hour time points, or with any pain score greater than 1 will be considered as failures.

The results to be presented for the analysis include those described in items (a) through (e) for the primary analysis of pain freedom (Section 5.7.3.1). In this case, the “risk” is the probability of sustained pain relief from 2 to 24 hours.

#### **5.7.4.8 Sustained Pain Relief from 2 to 48 Hours**

Sustained pain relief will be assessed using the number of subjects that experience no or mild headache pain (response of 0 or 1 on the 4-point Likert scale) at all time points from 2 through 24 hours post-dose. Subjects with missing pain scores at no more than 1 time point, given that

they have responses of no or mild pain at all other time points including the 2 hour time point will be considered as successes. Subjects with responses missing at more than 1 time point; with missing data at the 2 hour time point; or with any pain score greater than 1 will be considered as failures.

The results to be presented for the analysis include those described in items (a) through (e) for the primary analysis of pain freedom (Section 5.7.3.1). In this case, the “risk” is the probability of sustained pain relief from 2 to 48 hours.

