**NC1=F: Non-Completers with more than 1 missing data point = Failure.**

Subjects with more than 1 missing data point, other than at the 2, 24 or 48 hour data points, are classified as treatment failures. This applies to endpoints that are based on data from multiple time points. For example, for the durability endpoint of sustained pain freedom from 2 to 24 hours, the subjects should provide data at 2, 3, 4, 6, 8, and 24 hours. For NC1=F imputation, the data at 2 and 24 hour time points must be present or the subject is classified as a failure. However, any single data point may be missing at 3, 4, 6 or 8 hours without penalty. For sustained pain freedom from 2 to 48 hours, the data at 2, 24, and 48 hours are required to be present.

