**Table 2: Estimands for the Secondary Objectives**

Objective	Photophobia Freedom at 2 hours post-dose
Population	mITT subjects with photophobia reported as present at migraine onset
Variable	Percent of subjects reporting no photophobia at 2 hours post-dose
Intercurrent Events	NC=F; RM=F
Objective	Phonophobia Freedom at 2 hours post-dose
Population	mITT subjects with phonophobia reported as present at migraine onset
Variable	Percent of subjects reporting no phonophobia at 2 hours post-dose
Intercurrent Events	NC=F; RM=F
Objective	Pain Relief at 2 hours post-dose
Population	mITT
Variable	Percent of subjects who report mild or no pain at 2 hours post-dose
Intercurrent Events	NC=F; RM=F
Objective	Nausea Freedom at 2 hours post-dose
Population	mITT subjects with nausea reported as present at migraine onset
Variable	Percent of subjects reporting no nausea at 2 hours post-dose
Intercurrent Events	NC=F; RM=F
Objective	Probability of Rescue Medication
Population	mITT
Variable	Percent of subjects taking rescue medication
Intercurrent Events	None
Objective	Functional Disability at 2 hours
Population	mITT
Variable	Percent of subjects with a response of “normal” at 2 hours post-dose
Intercurrent Events	NC=F; RM=F
Objective	Sustained Pain Freedom (2 to 24 hours; or 2 to 48 hours)
Population	mITT
Variable	Percent of subjects pain free during the period of interest
Intercurrent Events	NC1=F; RM=F
Objective	Sustained Pain Relief (2 to 24 hours; or 2 to 48 hours)
Population	mITT
Variable	Percent of subjects who report no pain, or mild pain, during the period of interest
Intercurrent Events	NC1=F; RM=F
Objective	Pain Relapse (2 to 48 hours)
Population	mITT subjects who report pain freedom at 2 hours post-dose
Variable	Percent of subjects who report any pain during the period of interest
Intercurrent Events	NC1=F; RM=F

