#### **5.7.4.9 Pain Relapse from 2 to 48 Hours**

Pain relapse is assessed using the number of mITT subjects that are pain free at 2 hours post-dose as the denominator. The numerator is the number of these subjects that then have a relapse of pain at any severity (response of 1, 2, or 3 on the 4-point Likert scale) within 48 hours after administration of study medication. Subjects with more than 1 time point with missing data or with missing data at the 2, 24, or 48 hour time point are classified as relapsers.

The results to be presented for the analysis include those described in items (a) through (e) for the primary analysis of pain freedom (Section 5.7.3.1). In this case, the “risk” is the probability of sustained pain relapse from 2 to 48 hours.

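### SAP 5.7.4.8 defines sustained pain relief from 2 to 48 hours over a 2 to 24 hour window and requires only the 2 hour score, against the NC1=F rule assigned in Table 2

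*SAP*

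**What the plan says.** SAP 5.7.4.8 is headed as the 2 to 48 hour endpoint, and its last sentence says that the risk "is the probability of sustained pain relief from 2 to 48 hours". The success clause between them asks for a "response of 0 or 1 on the 4-point Likert scale) at all time points from 2 through 24 hours post-dose". One missing score is tolerated. The only missing score that by itself makes a subject a failure is the 2 hour score: those "with missing data at the 2 hour time point; or with any pain score greater than 1 will be considered as failures", as are those with more than one score missing.

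Table 2 defines sustained pain relief for both windows as "Percent of subjects who report no pain, or mild pain, during the period of interest", in mITT subjects, with NC1=F and RM=F. SAP 2.3 states NC1=F in general terms: "Subjects with more than 1 missing data point, other than at the 2, 24 or 48 hour data points, are classified as treatment failures". It adds: "This applies to endpoints that are based on data from multiple time points". Its worked examples, both for pain freedom, require the 2 and 24 hour scores for the 24 hour window, and the 2, 24 and 48 hour scores for the 48 hour window.

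The parallel 48 hour endpoints follow that rule. In 5.7.4.6 (pain freedom), subjects with "missing data at the 2, 24, or 48 hour time point; or with any pain score greater than 0 will be considered as failures". In 5.7.4.9 (pain relapse), subjects "with missing data at the 2, 24, or 48 hour time point are classified as relapsers". Section 5.7.4.7 (relief to 24 hours) requires the 2 and 24 hour scores. Appendix 4 section 1.2 (relief from 3 or 4 hours to 48 hours) requires the starting, 24 and 48 hour scores. Protocol 3.2 gives the window as 2 to 48 hours and is silent on missing scores.

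**The concern.** There are two separate departures. The first is the window, where the section contradicts its own heading and closing sentence, Table 2 and the protocol. The second is the set of mandatory scores, where the section is looser than the rule assigned to it and than every parallel definition. A reader who silently changes 24 to 48 repairs only the first.

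The endpoint is ninth in the fixed sequence of SAP 5.2.5, ahead of pain relapse and functional disability at 2 hours, and fourth in the meta-analysis sequence of SAP 5.7.5. A confirmatory test needs one responder definition. Here two programmers could derive different responders and each cite the SAP. A subject with no 48 hour score could be reported as having relief sustained to 48 hours. If item 9 changed between significant and not significant, the formal status of items 10 and 11 could change with it.

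**Working it through.** The plan gives no figure for this point, so the check applies each rule to every possible pattern of scores.

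**Inputs.** Scheduled scores from 2 to 48 hours (SAP 5.6): 2, 3, 4, 6, 8, 24 and 48 h, seven in all. Rules compared:

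- A: NC1=F for a 48 h window. At most one score missing; 2, 24 and 48 h present.
- B: 5.7.4.8 read over 2 to 48 h. At most one score missing; only 2 h required.
- C: 5.7.4.8 read over 2 to 24 h throughout, with the 48 h score ignored. This applies the 24 h limit to the failure clauses as well, where it is not printed.
- D: 5.7.4.7, the 2 to 24 h relief endpoint (item 7), for comparison. At most one score missing; 2 and 24 h required; 48 h ignored.

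**Missing-data patterns that can be a success.** Each score is present or missing, giving 2^7 = 128 patterns. Every observed score is taken as none or mild.

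- A: none missing, or one of 3, 4, 6, 8 h: 1 + 4 = **5**.
- B: none missing, or one of 3, 4, 6, 8, 24, 48 h: 1 + 6 = **7**. The 2 extra over A are 24 h alone and 48 h alone.
- C: none missing, or one of 3, 4, 6, 8, 24 h, with 48 h present or missing: (1 + 5) × 2 = **12**. The 7 extra over A are 24 h; 48 h; 48 h together with 3, 4, 6 or 8 h; and 24 with 48 h. Six of these 7 lack the 48 h score.
- D: (1 + 4) × 2 = **10**, all of them among the 12 of rule C. The other 2 lack the 24 h score.

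**Allowing moderate or severe pain.** With three states per score (none/mild, moderate/severe, missing) there are 3^7 = 2187 patterns. A and B still pass 5 and 7. C ignores the state at 48 h and passes 6 × 3 = 18; D passes 5 × 3 = 15. The 18 − 5 = 13 that C adds to A are 6 with moderate or severe pain at 48 h, 6 with 48 h missing, and 1 with 24 h missing and 48 h none or mild.

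**Four example subjects** (other scores none or mild):

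| Subject | A: NC1=F | B: 5.7.4.8 to 48 h | C: 5.7.4.8 to 24 h | D: 5.7.4.7 |
|---|---|---|---|---|
| 48 h missing | failure | success | success | success |
| 24 h missing | failure | success | success | failure |
| 8 h and 48 h missing | failure | failure | success | success |
| Moderate pain at 48 h | failure | failure | success | success |

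The second row shows the inconsistency most plainly. On either reading of 5.7.4.8, a subject missing only the 24 h score fails the 24 h endpoint but passes the 48 h one.

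**Direction.** Every pattern that passes A also passes B and C. Replacing B or C by A can therefore only lower each arm's success rate or leave it unchanged. The sign of the change in the risk difference is not determined.

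**The case against.** The strongest reply is that this is an obvious slip. The heading, the closing sentence, Table 2, the testing order, the meta-analysis list, the output title and protocol 3.2 all say 48 hours, and nothing outside the one clause supports 24. Appendix 4 section 1.2 also describes its later relief endpoints as similar to the existing 2 to 48 hour endpoint, and then requires the 24 and 48 hour scores. That is indirect evidence that the intended rule was the stricter one. This stands as evidence of intent. It does not amend 5.7.4.8, to which Appendix 4 section 1 refers back for the definition, and correcting the window leaves the second departure in place.

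Two narrower objections are fair. First, the general NC1=F sentence does not say in so many words that a missing 24 or 48 hour score is a failure; the worked examples do, and they name pain freedom. Applying that requirement to pain relief is an inference through Table 2, though the only sensible one given the parallel definitions. Second, the failure clauses of 5.7.4.8 carry no printed 24 hour limit. Applied without one, they catch moderate or severe pain at 48 hours and two missing scores, and 7 patterns pass, not 12. The 12 therefore depends on reading the whole paragraph as limited to 24 hours. The 2 extra patterns do not: they arise on either reading.

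It is also fair that this is a late secondary endpoint and that pattern counts say nothing about how many subjects are involved.

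**Conclusion.** The concern holds. Section 5.7.4.8 misstates the window and omits two of the three mandatory scores for an endpoint in the controlled testing sequence. It admits 2 missing-data patterns that NC1=F excludes if read to 48 hours, and 7 if read to 24 hours throughout; in the latter case moderate or severe pain at 48 hours is ignored as well, and the endpoint becomes a slightly looser copy of item 7.

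The conclusion assumes that NC1=F, as assigned in Table 2, is the intended rule. The co-primary tests, the order of testing and the Type I error control are not affected. The size and direction of any effect on the treatment comparison cannot be computed, because the documents give neither missing-score rates nor pain rates at 48 hours by arm, and they do not show which rule was programmed. The tabulation of missing pain scores by time point and arm planned in SAP 5.6 would give an upper bound on the number of subjects affected through a missing 24 or 48 hour score.

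**What to change.** Rewrite 5.7.4.8 for mITT subjects along these lines:

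- Success: pain of none or mild at every scheduled assessment between 2 and 48 h, with no more than one score missing, and that one only at 3, 4, 6 or 8 h.
- Failure: a missing score at 2, 24 or 48 h; more than one missing score; any score above 1 between 2 and 48 h; or rescue or other headache medication at or before the 48 h assessment, including the plan's existing rule for a missing time of intake.

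This uses only rules already in the plan: NC1=F, RM=F, Table 2, 5.7.1 and 5.7.4.6. Then confirm which rule was programmed for item 9, check whether the fourth meta-analysis test uses the same derivation, and record the correction as a dated SAP clarification.

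The cost is one paragraph and a check of one derivation; the 24 and 48 hour scores are already collected. If NC1=F was programmed, the reported rates do not change. If either reading of 5.7.4.8 was programmed, item 9 must be re-run. Its rates can then only stay the same or fall in each arm, and the standing of items 10 and 11 must be checked again. Since SAP version 2.0 adds post-hoc analyses, largely described in the past tense, such a re-run may alter a result already produced and should be disclosed with the reason.

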#### **5.7.4.9 Pain Relapse from 2 to 48 Hours**

Pain relapse is assessed using the number of mITT subjects that are pain free at 2 hours post-dose as the denominator. The numerator is the number of these subjects that then have a relapse of pain at any severity (response of 1, 2, or 3 on the 4-point Likert scale) within 48 hours after administration of study medication. Subjects with more than 1 time point with missing data or with missing data at the 2, 24, or 48 hour time point are classified as relapsers.

The results to be presented for the analysis include those described in items (a) through (e) for the primary analysis of pain freedom (Section 5.7.3.1). In this case, the “risk” is the probability of sustained pain relapse from 2 to 48 hours.

#### **5.7.5 Durability Endpoints Evaluated by Meta-Analysis**

The durability endpoints (e.g., pain freedom from 2 to 24 hours) will be analyzed in a meta-analysis that uses the data from both BHV3000-301 and BHV3000-302. These endpoints will be tested in a fix sequence, in the order shown below, with each test conducted at a two-sided alpha level of 0.05.

1. Sustained Pain Freedom from 2 to 24 hours
2. Sustained Pain Relief from 2 to 24 hours
3. Sustained Pain Freedom from 2 to 48 hours
4. Sustained Pain Relief from 2 to 48 hours
5. Pain Relapse from 2 to 48 hours

For the durability endpoints, the meta-analysis will mirror the primary analysis, with the addition of strata to represent each study. The common risk difference is computed using CMH weights, stratified by the use of prophylactic migraine medication (yes or no) and study (BHV3000-301 or BHV3000-302). For each endpoint, the risk difference is tested at a two-sided alpha level of 0.05. If a stratum (prophylactic medication use: yes or no) has sparse data (less than 5 subjects) then the strata will be pooled.

Results presented for each analysis include the following:

- The number and percentage of subjects who are successes or not successes on the endpoint of interest. These are presented by strata and treatment group, with ASE, and 95% asymptotic CIs.
- Common risk difference with sample size, p-value, ASE, and 95% asymptotic CIs.
- Risk difference within each strata with sample size, p-value, ASE, and 95% asymptotic CIs.
- A plot of the risk differences within each strata and common risk difference.
- Common risk for each treatment with sample size, ASE, and 95% asymptotic CIs.
- The common risk difference, with ASE, is also computed separately for each of the two studies.

### **5.7.6 Exploratory Efficacy Endpoints**

Any p-values presented for exploratory efficacy endpoints are for descriptive purposes only.

#### **5.7.6.1 Functional Disability Scale at 24 Hours**

Data will be analyzed in the same manner as described in Section 5.7.4.4. However, in this case the analysis uses the data from the 24 hour post-dose time point.

#### **5.7.6.2 Pain Relief at 30, 60 and 90 Minutes Post-Dose**

Pain relief at 30, 60, and 90 minutes post-dose will be assessed by tabulating the number of mITT subjects that report a pain level of none or mild (responses of 0 or 1 on the 4-point Likert scale) at the specified post-dose time point by treatment group. Subjects with missing data at the specified post-dose time point will be imputed as failures (NC=F).

First, the data will be evaluated at each time point, using the first analysis methods described in Section 5.7.3.1.

Pain relief over time up to 2 hours will be analyzed using Kaplan-Meier methods. Kaplan-Meier estimates will be tabulated using the following time periods (0 through 30 minutes, > 30 through 60 minutes, > 60 through 90 minutes, > 90 through 135 minutes, and >135 minutes). For each time period, the number of subjects at risk, with an event (pain relief), censored, and survival probability estimate (with 95% CI), will be presented by treatment group. Subjects who never reach mild or no pain by 135 minutes, will be censored at 136 minutes. Additionally, subjects who take rescue medication prior to 135 minutes will be censored at the date/time associated with their rescue medication. Note that the probability of survival corresponds to the probability of NOT having pain relief. Survival estimates are calculated using the Kaplan-Meier product-limit method and median survival (time to pain relief), and will be presented along with 95% CIs calculated using the method of Brookmeyer and Crowley.

To support the analysis, a Kaplan-Meier plot, with time in minutes on the x-axis and probability of survival on the y-axis, will be presented by treatment group. The number at risk at each time point (0, 15, 30, 45, 60, 90, and 135) minutes will be presented below the figure. In this analysis, being at risk corresponds to not yet having had pain relief; therefore, the subject is still “at risk” of having pain relief. Once a subject has pain relief or is censored, then the subject is no longer in the risk pool. If a subject has missing data at an earlier time point, then the time point with missing data is not considered. The subject is still considered at risk of failure at a future time point if data are available. Subjects are censored as described above.

#### 5.7.6.3 *Preference of Medication (PoM)*

The PoM is a brief scale that captures the subjects’ perception of whether the medication they are taking has had a greater benefit compared with previous medications to treat their pain. Responses at 24 hours post-dose for all subjects who provided a response, and answered “yes” to the lead-in question (i.e. “Have you ever taken migraine medication”) will be tabulated. The number and percentage of subjects preferring the study medication, along with 95% asymptotic CIs, are presented by treatment group. The tabulations will be repeated for the subset of subjects considered as responders and non-responders by treatment group without imputation. Responders are those subjects who reported a pain score of 0 or 1 at 2 hours post-dose and who did not require rescue medication at or prior to 2 hours post-dose.

#### 5.7.6.4 *Migraine Quality of Life Questionnaire (MQoLQ)*

Impact of treatment on patient-reported quality of life is assessed using the MQoLQ, which is a 15-item instrument that has been validated in migraine patients to measure the short-term impact of treatment (within 24 hours). The MQoLQ consists of 15 items across the following five domains: (1) work functioning, (2) social functioning, (3) energy/vitality, (4) migraine symptoms, and (5) feelings/concerns. There are three items within each domain. Response options for each of the items are on a 7-point scale where 1 indicates maximum impairment of QoL and 7 indicates no impairment. Each domain has a maximum score of 21 and a minimum score of 3. The items in the work functioning domain are: (1) ability to do normal everyday work, (2) ability to operate machinery or a motor vehicle, and (3) ability to stay alert. The items in the social functioning domain are: (1) interactions with people who are close to you, (2) interactions with other people, and (3) ability to enjoy life. The items in the energy/vitality domain are: (1) energy level, (2) ability to have a good night's sleep, and (3) mood. The items in the migraine symptoms domain are: (1) have throbbing head pain, (2) have increased sensitivity to light and/or noise, and (3) have nausea. Lastly, the items in the feelings/concerns domain are: (1) feel upset about having migraine headaches, (2) feel physically uncomfortable, and (3) feel concern that your migraine medication wouldn't relieve your migraine headache symptoms.

The observed responses at 24 hours post-dose will be presented for each item, each domain, and as a total score, by treatment group. The observed responses at 24 hours will also be summarized as a continuous response for each item, domain, and for the total score. Responses will also be presented in a by-subject listing along with treatment group, historical MBS collected at screening, MBS reported at migraine onset, migraine severity just prior to study medication, and migraine severity at 24 hours post-dose.

